5.1 Primary Estimand

Primary Objective 2.3.1.1: To estimate the difference in neutralizing antibody (NAb) response to mRNA-based COVID-19 vaccine among participants with prior SARS-CoV-2 infection who received investigational therapy exposure compared to participants without prior investigational therapy exposure (placebo for investigational therapy).

Estimand description	Neutralizing antibody response measured at least 140 days after the first dose of the study- or community-provided mRNA-based COVID-19 vaccine in individuals who previously received therapy for COVID-19 (active therapy versus placebo) and who received at least one dose of an mRNA-based COVID-19 vaccine.
Treatment	
Cohort 1a: Moderna mRNA-1273 COVID-19 vaccine, 100 µg (0.5 mL) to be administered intramuscularly (IM) at Entry and Day 28. Both doses will be provided by the study.
 
Or
 
Cohort 1b: Participants will receive a two-dose series of a community-provided mRNA-based COVID-19 vaccine that has received FDA EUA or FDA approval (e.g., Moderna or Pfizer). Vaccine will not be provided by the study.
 
Or
 
Cohort 1c: Participants will receive their first Moderna mRNA-1273 COVID-19 vaccine dose in the community. Their second Moderna mRNA-1273 dose will be provided by the study (100 µg [0.5 mL] to be administered IM 28 days after their first dose).

Target population	Analysis sets
Individuals who received an mRNA-based COVID-19 vaccine who previously received therapy for COVID-19 infection.	ACTIV-2/A5401 active therapy/placebo Response set (All enrolled participants who were previously enrolled to active therapy or placebo in ACTIV-2/A5401 who received at least one dose of vaccine.)
Variables	Outcome measure
NAb level measured approximately 140 days after receiving the first dose of an mRNA-based vaccine for COVID-19.	Neutralizing antibody (NAb) level at least 140 days after the first vaccine dose.
Handling of intercurrent events	Handling of missing data

The following intercurrent events are relevant to the estimand:
 
 1. Reinfection with SARS-CoV-2 between first and second vaccine doses. Post-vaccination observations before reinfection will be used to determine the variable (while alive and prior to reinfection strategy) 2. Reinfection with SARS-CoV-2 after second vaccine dose. Post vaccination observations before reinfection will be used to determine the variable (while alive and prior to reinfection strategy) 3. Discontinuation of treatment after first vaccine dose due to safety event(s). 	
If the day 140 outcome is missing, we will use the value from day 56 (last observation carried forward method of imputation).
 
Participants missing both day 56 and day 140 study visit outcome data will be excluded from the analysis.
 
Sensitivity Analyses:
 
 1. We will impute the missing Day 140 outcome values using multiple imputation (if sufficient sample size) 2. We will only include participants who provided a Day 140 NAb measurement.

Post vaccination observations before discontinuation will be used to determine the variable (while alive and prior to discontinuation strategy)
 
4. Discontinuation of treatment after first vaccine dose due to non-safety reasons.
 
Post vaccination observations before discontinuation will be used to determine the variable (while alive and prior to discontinuation strategy)
 
5. Death prohibiting subsequent existence of the variable.
 
Observations before death will be used to determine the variable (while alive strategy)
	

Population-level summary measure
 
Geometric mean neutralizing antibody levels at 140 days after first dose of an mRNA-based COVID-19 vaccine.
	
Analysis approach
 
We will report the geometric mean NAb levels among each group:
 
 (1) Participants exposed to AZD7442 IM or IV, BRII-196+BRII 198 IV, SAB 185 (3,840 or 10,240 units/kg), BMS 096414+BMS 986413 subcutaneous in ACTIV-2/A5401 (2) Participants exposed to placebo in ACTIV-2/A5401 (3) Participants exposed to placebo or Camostat Oral in ACTIV-2/A5401 
Ratio of geometric mean neutralizing antibody levels comparing those who received select investigational therapy (AZD7442 IM or IV, BRII-196+BRII-198 IV, SAB 185 (3,840 or 10,240 units/kg), BMS 096414+BMS 986413 subcutaneous in ACTIV-2/A5401) relative to placebo at Day 140 study visit, together with corresponding 95% confidence interval. We will use the log base 10 scale for the analysis of NAb measurements and report the anti-logged estimates and confidence intervals. We assume that the NAb responses are approximately normally distributed on the log base 10 scale and so confidence intervals can be calculated using standard methods.
 
The analysis will be repeated comparing those who received select investigational therapy (AZD7442 IM or IV, BRII-196+BRII-198 IV, SAB 185 (3,840 or 10,240 units/kg), BMS 096414+BMS 986413 subcutaneous in ACTIV-2/A5401) relative to placebo or Camostat.

Supplemental Analyses

To allow for the possibility that the distribution of time from receipt of select investigational therapy or placebo to the first dose of vaccine may differ, an analysis adjusted for this time may also be undertaken if sample size permits.

If sample size permits, the same analyses will be carried out in subgroups defined by levels of sex, race/ethnicity, and mRNA vaccine (Moderna or Pfizer).

5.2 Key Secondary Estimand

Primary Objective 2.3.1.1: To estimate the difference in neutralizing antibody (NAb) response to mRNA-based COVID-19 vaccine among participants with prior COVID-19 who received investigational therapy exposure compared to participants without prior investigational therapy exposure (placebo for the investigational therapy).

Estimand description	Neutralizing antibody response measured before and at least 56 days after the first dose of the study- or community-provided mRNA-based COVID-19 vaccine in individuals who received at least one dose of an mRNA-based COVID-19 vaccine.
Treatment	
Cohort 1a: Moderna mRNA-1273 COVID-19 vaccine, 100 µg (0.5 mL) to be administered intramuscularly (IM) at Entry and Day 28. Both doses will be provided by the study.
 
Or
 
Cohort 1b: Participants will receive a two-dose series of a community-provided mRNA-based COVID-19 vaccine that has received FDA EUA or FDA approval (e.g., Moderna or Pfizer). Vaccine will not be provided by the study.
 
Or
 
Cohort 1c: Participants will receive their first Moderna mRNA-1273 COVID-19 vaccine dose in the community. Their second Moderna mRNA-1273 dose will be provided by the study (100 µg [0.5 mL] to be administered IM 28 days after their first dose).

Target population	Analysis set
Individuals who received an mRNA-based COVID-19 vaccine who previously received therapy for COVID-19 infection.	All enrolled participants who were previously enrolled to active therapy or placebo in ACTIV-2/A5401 who received at least one dose of vaccine and have a NAb level from before first vaccine dose and a NAb level from at least 56 days after the first dose of the vaccine.
Variables	Outcome measure

NAb level measured prior to receiving the first dose of an mRNA-based vaccine for COVID-19.
 
NAb level measured approximately 56 days after receiving the first dose of an mRNA-based vaccine for COVID-19.
	Relative pre-vaccine to post-vaccine change in NAb response defined as the ratio of post-vaccine level/pre-vaccine level. The pre-vaccine NAb measurement will be obtained before the first dose of the vaccine and the post-vaccine measurement will be obtained at least 56 days after the first dose of the vaccine.
Handling of intercurrent events	Handling of missing data

The following intercurrent events are relevant to the estimand:
 
 1. Reinfection with SARS-CoV-2 between first and second vaccine doses. Post vaccination observations before reinfection will be used to determine the variable (while alive and prior to reinfection strategy) 2. Reinfection with SARS-CoV-2 after second vaccine dose. Post vaccination observations before reinfection will be used to determine the variable (while alive and prior to reinfection strategy) 	
For participants who receive the first dose of vaccine prior to study entry, the pre-first vaccine dose NAb measurement will be missing and these individuals will be excluded from the analysis (per analysis set defined above).
 
If the day 56 study visit outcome is missing, we will use the value from the day 28 study visit (last observation carried forward method of imputation).
 
Participants missing both day 28 and day 56 study visit outcome data will be excluded from the analysis.

3. Discontinuation of treatment after first vaccine dose due to safety event(s). Post vaccination observations before discontinuation will be used to determine the variable (while alive and prior to discontinuation strategy)
 
4. Discontinuation of treatment after first vaccine dose due to non-safety reasons. Post vaccination observations before discontinuation will be used to determine the variable (while alive and prior to discontinuation strategy)
 
5. Death prohibiting subsequent existence of the variable. Observations before death will be used to determine the variable (while alive strategy)
	
Sensitivity Analyses:
 
 1. We will impute the missing outcome values 56 days after the first vaccine dose using multiple imputation. 2. We will only include participants who had NAb measurements at Entry and 56 days after the first vaccine dose.

Population-level summary measure
 
Relative change in geometric mean neutralizing antibody levels from before first vaccine dose to 56 days after first vaccine dose.
	
Analysis approach
 
We will report the relative change in geometric mean NAb levels among each group:
 
 (1) Participants exposed to AZD7442 IM or IV, BRII-196+BRII 198 IV, SAB 185 (3,840 or 10,240 units/kg), BMS 096414+BMS 986413 subcutaneous in ACTIV-2/A5401 (2) Participants exposed to placebo in ACTIV-2/A5401 (3) Participants exposed to placebo or Camostat Oral in ACTIV-2/A5401 
Ratio of change in geometric mean neutralizing antibody levels comparing those who received select investigational therapy (AZD7442 IM or IV, BRII-196+BRII-198 IV, SAB 185 (3,840 or 10,240 units/kg), BMS 096414+BMS 986413 subcutaneous in ACTIV-2/A5401) relative to placebo from before first vaccine dose to Day 56 study visit, together with corresponding 95% confidence interval. We will use the log base 10 scale for the analysis of NAb measurements and report the anti-logged estimates and confidence intervals. We assume that the NAb responses are approximately normally distributed on the log base 10 scale and so confidence intervals can be calculated using standard methods.
 
The analysis will be repeated comparing those who received select investigational therapy (AZD7442 IM or IV, BRII-196+BRII-198 IV, SAB 185 (3,840 or 10,240 units/kg), BMS 096414+BMS 986413 subcutaneous in ACTIV-2/A5401) relative to placebo or Camostat.

Supplemental Analyses

To allow for the possibility that the distribution of time from receipt of select investigational therapy or placebo to the first dose of vaccine may differ, an analysis adjusted for this time may also be undertaken if sample size permits.

If sample size permits, analyses will be carried out in subgroups defined by levels of sex and race/ethnicity.

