3.2 Secondary Outcome Measures

- 3.2.1** Relative pre-vaccine to post-vaccine change in NAb response defined as the ratio of post-vaccine level/pre-vaccine level. The pre-vaccine NAb measurement will be obtained before the first dose of the vaccine and the post-vaccine measurement will be obtained at least 56 days after the first dose of the vaccine. (Objective 2.3.1.1)
- 3.2.2** New Grade 3 or higher AE, or SAE, or AE leading to change or discontinuation in vaccine receipt from first dose of the mRNA-based COVID-19 vaccine and through 140 days after the first dose of vaccine. (Objective 2.3.2.1)
- 3.2.3** Grade 1 or higher allergic reaction from first dose of the mRNA-based COVID-19 vaccine through the visit 56 days after the first dose of the vaccine. (Objective 2.3.2.1)
- 3.2.4** Grade 2 or higher injection site reaction from first dose of the mRNA-based COVID-19 vaccine through the visit 56 days after the first dose of the vaccine. (Objective 2.3.2.1)
- 3.2.5** Relative pre-vaccine to post-vaccine change in NAb response defined as the ratio of post-vaccine level/pre-vaccine level by received vaccine, i.e., Moderna versus Pfizer. The pre-vaccine NAb measurement will be obtained before the first dose of the vaccine, and the post-vaccine measurement will be obtained at least 56 days after the first dose of the vaccine. (Objective 2.3.1.1)

4 General Considerations

The aim of this study is to describe immunologic responses to mRNA-based SARS-CoV-2 vaccine among individuals who previously received investigational therapy in ACTIV-2/A5401 for SARS-CoV-2 infection in comparison to individuals who received a placebo. As ACTIV-2/A5401 is expected to change from using a placebo control to an active control, this study's aim will also evolve to describe immunologic responses to mRNA-based SARS-CoV-2 vaccine among individuals who previously received investigational therapy in ACTIV-2/A5401 for SARS-CoV-2 infection in comparison to individuals who received an active control.

Estimates and confidence intervals for NAb will be obtained by using a log base 10 transformation on the PSV values, then using linear regression with an indicator variable for prior select COVID-19 therapy exposure versus placebo using standard methods, assuming that the \log_{10} NAb responses are approximately normally distributed within exposure group.

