4.1 Analysis Sets and subgroups

4.1.1 ACTIV-2/A5401 active therapy/placebo Response Set

All enrolled participants who were previously enrolled to active therapy or placebo in ACTIV-2/A5401 who received at least one dose of vaccine.

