7.8 Key Secondary Estimand

- Change in geometric mean neutralizing antibody levels from before first vaccine dose to 56 days after the first vaccine dose among
 - Participants exposed to AZD7442 IM or IV, BRII-196+BRII 198 IV, SAB 185 (3,840 or 10,240 units/kg), BMS 096414+BMS 986413 subcutaneous in ACTIV-2/A5401
 - Participants exposed to placebo in ACTIV-2/A5401
 - Participants exposed to placebo or Camostat Oral in ACTIV-2/A5401
- Ratio of change in geometric mean neutralizing antibody levels (comparing those who received select therapy relative to placebo) from before first vaccine dose to 56 days after the first vaccine dose, together with corresponding 95% confidence interval.
- Ratio of change in geometric mean neutralizing antibody levels (comparing those who received select therapy relative to placebo or Camostat) from before first vaccine dose to 56 days after the first vaccine dose, together with corresponding 95% confidence interval.

- Sensitivity analyses using multiple imputation for those with missing NAb measurement 56 days after the first vaccine dose (if sufficient sample size).
- Sensitivity analyses conducted only among participants who had NAb measurements at Entry and 56 days after the first vaccine dose.
- Supplemental analyses adjusting for time from receipt of select investigational ACTIV-2/A5401 therapy (active or placebo) to the first dose of vaccine (if sufficient sample size).
- Supplemental analyses among levels of sex and race/ethnicity(if sufficient sample size).

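### SAP 5.2 carries a Day 28 antibody value, planned before dose 2, into a Day 56 outcome whose analysis set and definition require a value at least 56 days after dose 1

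*SAP*

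**What the plan says.** SAP 3.2.1 defines the outcome as the ratio of post- to pre-vaccine NAb, where "the post-vaccine measurement will be obtained at least 56 days after the first dose of the vaccine". The analysis set in SAP 5.2 requires a pre-dose-1 value "and a NAb level from at least 56 days after the first dose of the vaccine". The population summary in 5.2 is the change from before dose 1 to Day 56.

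The missing-data cell of the same table states: "If the day 56 study visit outcome is missing, we will use the value from the day 28 study visit". It adds: "Participants missing both day 28 and day 56 study visit outcome data will be excluded from the analysis". For people vaccinated before entry, who lack a pre-dose-1 value, it says "these individuals will be excluded from the analysis (per analysis set defined above".

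Two sensitivity analyses are listed in SAP 7.8: "Sensitivity analyses using multiple imputation for those with missing NAb measurement 56 days after the first vaccine dose (if sufficient sample size") and "Sensitivity analyses conducted only among participants who had NAb measurements at Entry and 56 days after the first vaccine dose".

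SAP 2.1 and Protocol LOA #1 (Section 3.0 and the legend to Figure 3.0-1) place the second blood draw before dose 2, if feasible: about 28 days after dose 1 for Moderna and about 21 days for community-given Pfizer. SAP 6.1.1 compares Moderna with Pfizer by following 5.2.

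**The concern.** A participant with a Day 28 value and nothing later is outside the 5.2 analysis set but inside the analysis that the missing-data rule describes. The value carried forward is, as planned, a response to one dose, yet it would count as the response at Day 56, after the planned two-dose series. If NAb changes between the two visits, each affected group's fold-rise is misstated. If substitutions are unevenly spread, the between-group ratio moves as well.

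The Moderna/Pfizer ratio is the more exposed. In Protocol LOA #1, Table 6.1-3 (community vaccine) has a visit on the day of dose 2 and no Day 28 visit, so the rule is undefined for those participants, Pfizer recipients among them. SAP 7.10 lists no observed-value sensitivity analysis for this ratio.

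**Working it through.** **Step 1. Set the parts of 5.2 side by side.**

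| Part | Day 28 value only | Day 140 value, no Day 56 |
|---|---|---|
| Analysis set | Out | In, read literally |
| Outcome measure | Not met | Met by Day 140, read literally |
| Missing-data rule | In, using Day 28 | Day 28 used if present, over a later value |
| Summary measure (Day 56) | Not the stated time point | Not the stated time point |

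**Step 2. Is the rule meant to operate?** Mainly, yes. The exclusion is limited to people missing both visits. Both sensitivity analyses also need people without a Day 56 value in the main analysis. If the set admitted only those with an observed Day 56 value, there would be nothing to impute, and the observed-value analysis would repeat the main one. The reference back to the analysis set concerns only the missing pre-dose-1 value, so it does not settle the matter the other way.

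**Step 3. Intercurrent events.** The 5.2 column uses values from before reinfection, discontinuation or death. For an event between Day 28 and Day 56, that value is Day 28. The analysis set admits nobody on that value alone, so these two parts do not fit either.

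**Step 4. Moderna versus Pfizer.** Read literally, a Day 28 visit exists only in the schedules for fully study-provided vaccine, which is Moderna, so no Pfizer value could be substituted. Read loosely as the pre-dose-2 visit, the rule uses about Day 21 for Pfizer and about Day 28 for Moderna. Both readings treat the vaccines differently.

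**Step 5. Reproduce the plan's precision.** Inputs from SAP 2.4: SD 0.4 (taken as log10 scale), 35 per group, observed ratio 1. The 95% limits are 10^(±t(0.975, 2n−2) × 0.4 × √(2/n)).
- n = 35: factor 1.552, limits 0.644 to 1.552. The SAP gives 0.64 to 1.55, so the method reproduces it.
- n = 10 (assumed): factor 2.376, limits 0.42 to 2.38.
- n = 5 (assumed): factor 3.832, limits 0.26 to 3.83.

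The documents give 43 enrolled in total, not the size of each arm of this analysis.

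**Step 6. Size of a substitution.** Let k be the Day 56 level divided by the Day 28 level and m the number of substituted values among n in an arm. The arm's geometric mean fold-rise is multiplied by k^(−m/n). With n = 10:

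| k (assumed) | m = 1 | m = 2 |
|---|---|---|
| 0.5 | 1.072 | 1.149 |
| 1 | 1.000 | 1.000 |
| 2 | 0.933 | 0.871 |
| 3 | 0.896 | 0.803 |
| 5 | 0.851 | 0.725 |

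If only one arm has substitutions, the between-group ratio is multiplied by the same factor or its inverse (for m = 2 and k = 5: 0.725 or 1.380). With equal m, n and k in both arms the ratio does not move. Every factor shown lies within 0.42 to 2.38.

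**Step 7. The primary estimand.** In SAP 5.1 the analysis set is "All enrolled participants who were previously enrolled to active therapy or placebo in ACTIV-2/A5401 who received at least one dose of vaccine", so carrying Day 56 to Day 140 does not conflict with that set. But its outcome (SAP 3.1.1 and 5.1) is worded as at least 140 days after dose 1. Protocol LOA #1, item 9 (Section 10.6), defines the primary analysis population by a response at least 140 days after dose 1. A milder parallel therefore exists; both visits are planned after dose 2.

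**The case against.** The best defence is that the rule is clear in operation and the analysis set is the part that is out of line. Carry-forward fits the intercurrent-event column, the exclusion of those missing both visits and the two sensitivity analyses. Widening the set to a pre-dose-1 value plus Day 28 or Day 56 would then be the smaller repair and would need no re-run.

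Much of this stands. A reader might infer that the SAP leaves wholly open which part governs; the documents do not support that, because most of 5.2 points to the substitution operating. But widening the set would not finish the repair. The outcome measure would still require at least 56 days, the summary would still be the change to Day 56, and a pre-dose-2 sample would still enter as that value.

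The harm is also limited. SAP 2.3 makes the objectives descriptive and dependent on sample size, SAP 2.4 already warns of low precision at 20 or 30 participants, and the observed-value sensitivity analysis removes every substituted value from the key secondary outcome. One could argue that 6.1.1 imports that analysis by following 5.2, but 7.10 does not list it.

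**Conclusion.** The contradiction holds and should be fixed: as written, 5.2 lets a sample planned before dose 2 stand for the Day 56 response, against its own set, outcome and summary, and 6.1.1 inherits this with a visit that community-vaccinated participants do not have.

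Three stronger conclusions are tempting and unsupported.
- That the reported estimate is biased: the documents do not show that any value was substituted, and the effect is zero if none was.
- That the error runs against prior therapy: the between-group ratio can move either way, or not at all.
- That the primary analysis is either free of the problem or equally affected: it has no conflict with its SAP set, but it does not match its own outcome wording or the protocol population, and its carry-forward does not cross dose 2.

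The illustrated shifts rest on assumed arm sizes, substitution counts and values of k. They lie inside the expected CI, which limits the practical weight of the point but does not reconcile the text.

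**What to change.** 1. In 5.2 and 6.1.1, make the analysis of observed pre-dose-1 and Day 56 values the main one. Specify pre-dose-1 rather than entry, because community-vaccine participants may enter after dose 1. Keep Day 28 carry-forward only as a labelled sensitivity analysis, and state how it applies where the schedule has no Day 28 visit.
2. Align the analysis set, outcome wording and intercurrent-event column with this. Check the outcome wording against the full protocol and CM #1, since a change there may need more than an SAP edit.
3. SAP 1.2 says the final report was run under v3.0. Report the number of substituted values per group and per vaccine. If it is zero, correct only the wording. Otherwise show both versions and label the change post hoc.
4. Reconcile the primary analysis set and carry-forward in SAP 5.1 with the population in protocol Section 10.6 as revised by LOA #1.

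Cost: SAP text, a count and, if any value was substituted, a re-run of two estimates; the observed-value analysis of the key secondary outcome is already specified. Participants with only a Day 28 value, including some who stopped after dose 1, leave the main analysis, which then no longer covers everyone with at least one dose. The CI widens slightly: by the Step 5 formula, the 95% factor goes from 2.38 to 2.51 if an assumed 10 per arm falls to 9, and to 2.69 if it falls to 8.

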 - II. Fourth paragraph: “If sufficient Phase II participants in the A5401/ACTIV-2 trial from a select therapy group ~~at selected sites~~ are not able to be enrolled, then Phase III participants in the A5401/ACTIV-2 trial from that select therapy group ~~at selected sites~~ can be enrolled until full enrollment is achieved. However, Phase II participants are preferred.”
 - c. Section 4.1.3: “For participants who are in, or who have completed, the ACTIV-2/A5401 trial: Receipt of all selected investigational therapy or active comparator/placebo for that therapy ~~at selected sites~~.”
2. Window for receipt of mRNA-based COVID-19 vaccine for ACTIV-2/A5401 participants

The window for receipt of the mRNA-based COVID-19 vaccine for ACTIV-2/A5401 participants was changed from 60-240 days to **30-240** days after their last dose of a select ACTIV-2/A5401 investigational therapy. This change is reflected in the following sections:

- a. Schema, Design Section
The second sentence of the third paragraph: “Participants in ACTIV-2/A5401 will receive their mRNA-based COVID-19 vaccine ~~6030~~-240 days after receiving their last dose of a select ACTIV-2/A5401 investigational therapy, or its comparator.”
- b. Section 2.2 Rationale, sub-section Reinfection
The third sentence of the second paragraph: “The optimal timing of a vaccination to boost such waning immunity is unknown and is the rationale for the ~~6030~~-240-day window after receiving their last dose of ACTIV-2/A5401 select therapy (i.e., post-infection) for vaccination in the proposed study.”

c. Section 3.0 Study Design

I. The second sentence of the second paragraph, "ACTIV-2/A5401 participants will be offered the Moderna mRNA-1273 COVID-19 vaccine or receive an mRNA-based COVID-19 vaccine in the community **60**30-240 days after receiving their last dose of ACTIV-2/A5401 select therapy (investigational agent or active comparator or placebo)."

II. Figure 3.0-1 was replaced with the figure below:

[figure not shown]

Figure 3.0-1: This schema includes common assessments for ACTIV-2/A5401 participants in both phases 2 and 3 (panel A). If possible, blood will be collected before each vaccine dose is administered and 56, 140, 365, and 730 days after **their first vaccine dose** (panel B). If possible, participants will be contacted 7 days after each vaccine dose to grade vaccine-associated symptoms.

d. Section 4.1 Inclusion Criteria

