7.3 Baseline Characteristics

- Summary of age, sex, gender, race, ethnicity, and BMI
- Summary of baseline NAb level

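### The key secondary NAb fold-rise ratio cannot be separated from a between-group difference in pre-vaccine NAb, because neither Day 56 levels by group nor a baseline-adjusted analysis is listed

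*SAP*

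**What the plan says.** The key secondary outcome in SAP 5.2 is "Relative pre-vaccine to post-vaccine change in NAb response defined as the ratio of post-vaccine level/pre-vaccine level". It is summarised as "Relative change in geometric mean neutralizing antibody levels from before first vaccine dose to 56 days after first vaccine dose", and the two exposure groups are compared by the ratio of these changes with a 95% confidence interval.

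SAP section 4 gives the model: log10 transformation, "then using linear regression with an indicator variable for prior select COVID-19 therapy exposure versus placebo using standard methods". On that scale the pre-vaccine value enters only as the quantity subtracted, so its coefficient is fixed at 1.

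The other analyses listed for this estimand (SAP 5.2 and 7.8) are:
- two sensitivity analyses, both about missing data;
- a repeat of the comparison with Camostat added to placebo;
- an adjustment for time from therapy to first dose, if sample size permits;
- subgroups by sex and race/ethnicity, if sample size permits.

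SAP 7.8 reports changes and ratios of changes. SAP 7.7 reports Day 140 levels. Absolute Day 56 levels by group appear in neither. SAP 7.3 lists a "Summary of baseline NAb level" without saying which sample is the baseline.

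**The concern.** A fold-rise has two parts. When two groups start from different levels, their fold-rises can differ although participants with the same starting level respond equally to the vaccine. This happens whenever the slope of post on pre (log10) is below 1.

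Pre-vaccine NAb is unlikely to be negligible here. Everyone in the comparison was previously infected, and Letter of Amendment #1 allows vaccination from 30 days after the last dose of study agent (previously 60). It also describes vaccination as boosting existing immunity: "The optimal timing of a vaccination to boost such waning immunity is unknown". A between-group difference could come from residual activity of the study agent, from a different antibody response to the infection under treatment, or from chance in a small, non-randomized comparison.

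At stake is the reading of the result. A ratio below 1 could be taken as therapy impairing vaccine response when it reflects a higher starting level. A ratio above 1 could be taken as enhancement, or could hide a real reduction, when the exposed group started lower.

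**Working it through.** **1. Reproduce the plan's precision (SAP 2.4).** Inputs: SD of change 0.4, 35 v 35, observed ratio 1. The interval is 10^(±t × SD × √(2/35)) with 68 df.
- 95%: 1.9955 × 0.4 × √(2/35) = 0.191, giving 0.64 to 1.55, as stated.
- 90%: 1.6676 × 0.4 × √(2/35) = 0.160, giving 0.69 to 1.44, as stated.
- With SD 0.5, the stated primary intervals (0.63 to 1.58; 0.58 to 1.73) also reproduce.

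So the SDs are on the log10 scale. The intervals cover sampling error only.

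**2. Shift from unequal starting levels.** Let D be the exposed-minus-placebo difference in mean log10 pre-vaccine NAb, and β the slope of post on pre, common to both groups. With equal response at a given starting level, the expected ratio of fold-rises is 10^((β − 1) × D). It is 1 if D = 0 or β = 1, below 1 if D > 0 and β < 1, and above 1 if D < 0 and β < 1.

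**3. A slope consistent with the SAP's SDs.** The SAP gives SD 0.5 for the level (stated for Day 140; using it for Day 56 is an assumption) and 0.4 for the change. The pre-vaccine SD is not given; assume 0.5.
- β = (0.5² + 0.5² − 0.4²) / (2 × 0.5²) = 0.34 / 0.50 = 0.68.
- Exposed 2-fold higher: 2^(−0.32) = 0.80.
- Exposed 3-fold higher: 3^(−0.32) = 0.70.
- Exposed 2-fold lower: 2^(0.32) = 1.25.

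Range for the 2-fold-higher case:

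| Assumed pre-vaccine SD | β | Fold-rise ratio |
|---|---|---|
| 0.4 | 0.78 | 0.86 |
| 0.5 | 0.68 | 0.80 |
| 0.7 | 0.59 | 0.75 |

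**4. Imbalance by chance.** With pre-vaccine SD 0.5 and illustrative groups of 15 v 15, the standard error of D is 0.5 × √(2/15) = 0.183. Then log10(2) / 0.183 = 1.65, so a 2-fold or larger imbalance, in either direction, occurs in about 10% of studies. At 10 v 10 it is about 18%.

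**5. What adjustment achieves.** With a common slope (simulation, pre-vaccine SD 0.5, change SD 0.4, slope 0.5, D = 0.3, 15 v 15), the unadjusted ratio averaged 0.71 and its 95% interval excluded 1 in 17% of runs. The model with log10 pre-vaccine NAb as covariate averaged 0.99 to 1.02 across all settings, and its interval excluded 1 in 4 to 6% of runs.

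**6. Where adjustment fails.** Suppose the exposed group carries passive product activity that adds to the participant's own antibody. Assume that it equals the own level (or, as a fixed amount, the typical own level) at vaccination, that 25 to 75% remains at Day 56, and that the own fold-rise is 5 to 20 with slope 0.68 and equal vaccine response. The adjusted ratio is then 0.53 to 0.74, still well below 1. The absolute Day 56 ratio is 1.02 to 1.25. Here the absolute levels warn the reader; the covariate does not.

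**The case against.** Several counter-arguments have force.

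- **Fold-rise is a declared estimand.** Change score and baseline adjustment answer different questions in non-randomized groups. This stands: the ratio should be kept and supplemented, not replaced.
- **Direction is not shown.** A reader might infer that carried-over activity makes the exposed group look like poorer responders, or that the primary and key secondary contrasts are biased in opposite directions. The documents do not support either. They give no pre-vaccine NAb by group and no figure for activity left by the agents. Antibody from infection is common to both groups and matters only if it differs between them.
- **The plan handles part of this.** The primary estimand is an absolute Day 140 level, and section 7 asks for all tables by therapy group, so some baseline NAb comparison is likely to appear. However, baseline is undefined, and Cohort 1b may enter after one or both doses and Cohort 1c after the first. A summary at entry would therefore mix pre- and post-vaccine values, and would not match the 5.2 analysis set. The adjustment for time since therapy is optional and only indirect.
- **Noise dominates.** The study is descriptive, enrolled 43 in total, and loses from 5.2 anyone vaccinated before entry. With SD 0.4 the 95% interval at ratio 1 is 0.42 to 2.38 for 10 v 10 and 0.50 to 1.99 for 15 v 15, so a shift to 0.80 lies well inside it. This limits over-reading, but a wide interval does not correct a shifted estimate or show its source.

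**Conclusion.** The point holds as a conditional one. The SAP compares fold-rises with the pre-vaccine coefficient fixed at 1, lists no analysis that relaxes this, and lists no Day 56 levels by group. A fold-rise ratio away from 1 therefore cannot be traced to numerator or denominator from the listed outputs.

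The illustrative size is 0.80 for a 2-fold higher starting level (0.86 to 0.75 for pre-vaccine SDs of 0.4 to 0.7) and 1.25 for a 2-fold lower one. This rests on an assumed imbalance, an assumed pre-vaccine SD, the Day 140 SD applied to Day 56, and a common slope. None of these shows that the result is biased, or in which direction. The improvement is worth making because it is cheap and changes what the ratio can support.

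**What to change.** In SAP 5.2 and 7.8, using the same analysis set and the same Day 56 value that enters the ratio:

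1. Report beside the fold-rise ratio the group geometric means, and their ratios with 95% confidence intervals, for pre-first-dose NAb and for absolute Day 56 NAb.
2. Add a supplemental regression of log10 Day 56 NAb on exposure group with log10 pre-first-dose NAb as covariate.
3. State that a fold-rise ratio below 1 is not by itself evidence of impaired vaccine response when the pre-vaccine ratio is above 1 and the absolute Day 56 ratio is not below 1.
4. State that the adjusted ratio does not remove carry-over of passive product activity, because the pre-vaccine level is measured after therapy and slopes may differ by group.

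In SAP 7.3, define baseline NAb as the value before the first vaccine dose.

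SAP 1.2 says that the final analysis report was conducted under version 3.0, so anything added after that report should be labelled post hoc.

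Cost: a few table rows and one degree of freedom in a small set. The analysis-set definition already requires both measurements, so no new data are needed. No gain in precision should be claimed from a 35 v 35 calculation, since only 43 participants were enrolled in all.
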